RESEARCH PROTOCOL

Reducing Diagnostic Error to Improve Patient Safety in COPD and Asthma (REDEFINE Study)

Version: 1.5

Date: 1/11/2018

Principal Investigator: [name] MD MPH

Division of Pulmonary, Critical Care, Sleep, and Allergy, Department of Medicine, University of Illinois at Chicago, Chicago, IL

Sponsor: AHRQ 1R01HS024964-01

SPECIFIC AIMS AND HYPOTHESIS

Aim 1: Determine the prevalence of and characteristics associated with diagnostic error (DE) in asthma and/or COPD in an underserved population

Aim 2: Evaluate the effectiveness of the REDEFINE program compared to usual care on health care utilization and patient-centered outcomes (including respiratory medication use, all-cause emergency room visits, and all-cause hospitalizations)

Hypothesis:

The REDEFINE program will reduce health care utilization and improve patient-centered outcomes compared to usual care.

Aim 3: Evaluate the cost impact and cost effectiveness of the REDEFINE program versus usual care

Hypothesis:

The REDEFINE program will be cost-effective in the management of patients with COPD and asthma compared to usual care.

BACKGROUND AND SIGNIFICANCE

Asthma and chronic obstructive pulmonary disease (COPD) are common chronic lung diseases that are diagnosed in more than 30 million adults in the United States.^{1,2} However, diagnostic error (DE), considered one of the most common and harmful of patient-safety problems by the Institute of Medicine,^{3,4} occur frequently with asthma and/or COPD and disproportionately affect minorities and the underserved. DE leads to lost opportunities to identify other chronic conditions, avoidable morbidity and mortality, unnecessary costs to patients and health systems, and poor quality of care.³⁻⁶ Shortness of breath or dyspnea, which is a common symptom in asthma and COPD, is also common for many other chronic conditions such as cardiovascular disease and obesity. A better understanding of the impact of DE and interventions to improve diagnostic accuracy in asthma and COPD are of particular importance for minorities and the underserved that are disproportionately affected by conditions leading to dyspnea.

Spirometry is a simple, mobile, and essential test that is recommended by all major national and international guidelines for the diagnosis of asthma and COPD.⁷⁻¹⁰

However it is well known that spirometry is not routinely used in the ambulatory primary care setting¹¹⁻¹⁹ and minorities and the underserved population are less likely to have spirometry leading to greater prevalence of DE.²⁰⁻²⁵ It has been estimated that 30-50% of people with an existing diagnosis of asthma and COPD were found to be misdiagnosed.^{11,20,21,26-32} Many of these patients misdiagnosed with asthma and/or COPD receive unnecessary respiratory pharmacotherapy which can pose serious risks including pneumonia, cardiovascular events, and mortality.³³⁻⁵³ In the setting of DE, these are considered avoidable and unnecessary respiratory pharmacotherapy use in minorities and the underserved that are already disproportionately affected by cardiovascular disease⁵⁴⁻⁵⁶ increases the risk of poorer outcomes. There is also DE in the diagnosis of asthma versus COPD, as these are both clinically distinct respiratory disorders with nuances in treatment recommendations. It is reported that African-Americans are considered to have increasing COPD mortality and are disproportionately affected by asthma death rates.⁵⁷⁻⁶⁰ However, as spirometry is not routinely performed and DE is prevalent in asthma and COPD, a component of these poor outcomes may be attributable to missed or delayed diagnoses of other chronic conditions or misdiagnosis within asthma and COPD.

Barriers to the use of spirometry in primary care exist at provider and health systems levels. Previous studies show that primary care providers (PCPs) lack knowledge in existing guidelines and in implementing spirometry into primary care clinics.^{11,18,61-64} Beyond these barriers, PCPs struggle with logistical challenges such as time and workflow constraints with clinic visits lasting 15 minutes or less in patients with multiple chronic medical conditions.^{62,65} These predisposing and enabling factors explain why prior studies that included interventions to educate PCPs and incorporate spirometry by training personnel in primary care clinics have had limited results.^{32,63,66-68}

A new paradigm to improve guideline based care for asthma and COPD which includes spirometry is needed and can lead to a better understanding of DE and improved patient safety and patient-centered outcomes. Health Promoters or Community health workers (CHWs) have been supplementing medical care by disseminating appropriate health care practices for underserved minority populations. However, studies which include diagnostic evaluations with spirometry for asthma and COPD have not been performed. The REDEFINE program (Reducing Diagnostic Error to Improve Patient SafEty in COPD and Asthma) will incorporate health promoters working collaboratively with PCPs to address identified barriers to guideline based care which includes spirometry for the diagnosis of asthma and COPD for patients at risk for DE. We propose a comparative effectiveness study to better understand the epidemiology of DE and to evaluate the effectiveness and economic impact of providing the REDEFINE program to an underserved, predominantly minority population with a diagnosis of asthma and/or COPD at risk for DE.

RESEARCH DESIGN AND METHODS

1. RESEARCH DESIGN

This will be a cluster-randomized comparative effectiveness trial conducted of patients with a primary care provider (PCP) diagnosis of COPD and/or asthma seen in outpatient primary care provider clinics (i.e. Family Medicine, Miles Square Health Center, and Academic Internal Medicine) as well as the CRC (Clinical Research Center) at the University of Illinois Hospital and General Internal Medicine and Family Medicine Clinics

at Cook County Health and Hospitals Systems (CCHHS). Providers will be randomized and their patients who fulfill the inclusion criteria will receive the intervention or be in the usual care group. Adults with a clinician-diagnosed COPD and/or asthma at high risk for diagnostic error due to lack of spirometry will undergo the REDEFINE intervention or usual care based on the PCP randomization. Outcomes will be assessed every 3 months for up to one year.

2. ELIGIBILITY CRITERIA

A. Primary care provider (PCP) eligibility criteria:

Primary care providers (PCPs) will include physicians and nurse practitioners. PCPs specializing in internal medicine or family medicine with at least one half day per week outpatient clinic session at the following clinics will be eligible for the study:

- UI Health: Family Medicine (FM) clinics, Academic Internal Medicine (AIM) clinics
- Miles Square Health Center (MSHC)
- Clinical Research Center (CRC) at UIC
- Cook County Health and Hospitals Systems (CCHHS): General Internal Medicine (GIM) and Family Medicine

B. Patient eligibility criteria:

Inclusion criteria:

1. Age ≥ 40 years of age
2. Use of a maintenance respiratory medication and one of the following in the past year:
 - a. diagnosis of asthma
 - b. diagnosis of COPD, emphysema, or chronic bronchitis
3. No spirometry test performed in the past 3 years
4. Past or current smoker

Exclusion criteria:

- Unable to perform adequate spirometry
- Non-English speaking
- Pregnancy
- Plans to move from the Chicago area within the next year
- Seen by pulmonary or allergy specialist in the past 3 years
- Any terminal illness with a life expectancy of < 6 months
- Life threatening (e.g. Intensive care admission and/or use of mechanical ventilation) respiratory failure event in the past year

3. SUBJECT SELECTION, RECRUITMENT, AND INFORMED CONSENT

PCP Selection, Recruitment, and Informed consent

Primary care providers (PCPs) specializing in internal medicine or family medicine with at least one half day per week outpatient clinic will be included in the study. We

estimate a total maximum recruitment of 80 eligible PCPs from all sites (approximately 50 PCPs from UI Health and MSHC sites and approximately 30 PCPs from CCHHS). The recruitment will include a combination of paper letter and email invitations with endorsement from the clinic directors and other supervisors. A list of eligible PCPs will be obtained from each site from the clinic directors. A research introduction letter will be mailed to the qualifying practitioners as well as an email invitation sent to their email accounts. The letter and email will be sent simultaneously to ensure contact and will include a short introduction to why the research is being performed and a description of participants' roles in the study. Also included will be a contact number for those who would like to volunteer or who would like additional information. The letter will include a statement that there will be no penalty for not participating. The letter will also contain a postcard with a stamp, where the eligible PCP checks to agree to participate or decline to participate. The email will instruct them to reply by email to the same choices. If a response is not received in 2 weeks, a second recruitment letter and email will be sent followed by a postcard 2 weeks later. Once a PCP agrees to participate, informed consent will be obtained prior to initiation of any study procedures.

Patient Selection, Recruitment, and Informed consent

Approximately 500 patients will be recruited for this study from the FM, AIM, MSHC and GIM sites (A total of 250 from UI Health and MSHC sites and a total of 250 from CCHHS site). All sites use the same electronic medical record (EMR) system which is Cerner Powerchart. An Information Systems Specialists (ISS) from UI Health (including MSHC) and CCHHS will search the administrative data of their respective sites to provide a list of patients meeting the first three of the inclusion criteria listed above and are scheduled to be seen in PCP clinics or the CRC (Clinical Research Center at UIC), two weeks in the future. More specifically, using electronic health records, within the past 12 months, the following patients will initially be identified: age \geq 40 years and using at least one maintenance respiratory medication (e.g. long acting beta agonists (LABA), long acting anticholinergics (LAA), inhaled corticosteroids (ICS), phosphodiesterase-4 inhibitors (PDE-4i), and at least one of the following 1) diagnosis of asthma (ICD-9 493.xx or ICD 10 J45.xx), 2) diagnosis of COPD, emphysema, or chronic bronchitis (ICD-9 491.xx, 492.xx, 496 or ICD 10 J41.xx, J42.xx, J43.xx, J44.xx). In addition, our ISS will also only include those who have not had a current procedural testing (CPT) codes for spirometry (CPT codes: 94010, 94014, 94015, 94016, 94060, 94070, 94620) or completed order for spirometry testing in the past 3 years.

Medical charts of patients will be reviewed to prescreen for eligibility for the study. Participants who meet preliminary eligibility criteria will be mailed a patient recruitment letter informing them of the study and our intent to contact them by telephone to complete a phone screen approximately one week before the participants' scheduled primary care visit. The letter will be sent 2 weeks before the planned phone screen and will have a phone number to call to opt out of the study. A patient phone screen is conducted to confirm eligibility criteria and the participants' verbal consent to participate in the study is obtained. During the call, we will confirm their scheduled appointment date, go over the study, answer any questions, and if the subject agrees, conduct the phone screen to verify eligibility criteria. If eligible, they will be asked to participate in the study and if agreeable will be asked to come in 90 minutes before the clinic visit. Once a subject agrees to participate, informed consent will be obtained prior to initiation of any study procedures.

4. DESCRIPTION OF PROCEDURES

A) PCP Education and Randomization:

After obtaining PCP informed consent and prior to patient recruitment, a one hour educational session will be held for PCPs participating in the study. The purpose of this session is to provide education to PCPs about COPD, asthma, spirometry, and GOLD and GINA guidelines (GOLD=Global Initiative for Chronic Obstructive Lung Disease, GINA=Global Initiative for Asthma). The educational session will provide continuing medical education credit to those who attend. The learning objectives will be the following: 1) Review COPD and asthma disease definition, presentation, diagnosis and testing including spirometry, 2) be familiar with the GOLD and GINA guidelines and recommendations for therapy.

PCPs who consented to participate in the study and completed the education session will be randomized to have their patients who meet the study criteria receive the intervention or usual care.

B) Patient subject- Intervention:

On the day of the outpatient visit, subjects will be advised to arrive 90 minutes prior to their clinic visit in the same building as the clinic site or the CRC (Clinical Research Center at UIC). The following information will be collected and procedures will be performed:

1. Subject demographic and contact information
2. Co-morbid conditions
3. Smoking history
4. Medication history from patient and also from pharmacy used by subjects
5. A respiratory exacerbation history in the past year
6. Modified Medical Research Counsel (mMRC) dyspnea scale and COPD Assessment Test
7. Quality of life measures
8. Pre and post-bronchodilator (BD) spirometry
9. De-Escalation Spirometry Screener for patients de-escalating based on spirometry (See Based on spirometry findings)
10. De-Escalation Phone Script

Based on spirometry findings:

1. If the spirometry findings are consistent with COPD and/or asthma, the following will be provided to the provider and patient to have available during the clinic visit: a letter summarizing the interpretation of the findings using GOLD/GINA criteria with recommendations for initial guideline driven therapy based on GOLD/GINA guidelines. Subjects will be managed by their PCP thereafter.
2. If the spirometry findings are normal, with approval from the PCP, will de-escalate respiratory medication therapy via a stepwise process and schedule patient back for a repeat pre and post bronchodilator spirometry within 1-2 weeks at the same time and place as the PCP clinic session or the CRC (Clinical Research Center at UIC). Again with the PCP approval, this

deescalation and repeat spirometry can occur in 1-2 week intervals until all maintenance medications are discontinued as long as the pre and post spirometry continues to be normal. After each visit, the following will be provided to the provider and patient: a letter summarizing the interpretation of the findings using GOLD/GINA criteria with recommendations for initial guideline driven therapy based on GOLD/GINA guidelines, if appropriate. Subjects will be managed by their PCP thereafter.

3. All spirometry test results and the subject's assessment at the time of the test will be uploaded into the subject's electronic health record for future reference.

C) Patient subject- Usual Care:

On the day of the outpatient visit, subjects will be advised to arrive 60 minutes prior to their clinic visit in the same building as the clinic site or the CRC (Clinical Research Center). The following will be performed.

1. Subject demographic and contact information
2. Co-morbid conditions
3. Smoking history
4. Medication history from patient and also from pharmacy used by subjects
5. A respiratory exacerbation history in the past year
6. Modified Medical Research Counsel (mMRC) dyspnea scale and COPD assessment test
7. Quality of life measures

Subjects will be advised to go to their clinics and be managed by their PCP thereafter.

At the end of the 1 year followup, the patient will be scheduled for a pre and post BD spirometry and undergo the same spirometry protocol (de-escalation protocol) as the intervention group.

Based on spirometry findings:

1. If the spirometry findings are consistent with COPD and/or asthma, the following will be provided to the provider and patient: a letter summarizing the interpretation of the findings using GOLD/GINA criteria with recommendations for initial guideline driven therapy based on GOLD/GINA guidelines. Subjects will be managed by their PCP thereafter.
2. If the spirometry findings are normal, with approval from the PCP, will de-escalate respiratory medication therapy via a stepwise process and schedule patient back for a repeat pre and post bronchodilator spirometry within 1-2 weeks at the same time and place as the PCP clinic session. Again with the PCP approval, this deescalation and repeat spirometry can occur in 1-2 week intervals until all maintenance medications are discontinued as long as the pre and post spirometry continues to be normal. After each visit, the following will be provided to the provider and patient: a letter summarizing the interpretation of the findings using GOLD/GINA criteria with recommendations for initial guideline driven therapy based on GOLD/GINA guidelines, if appropriate. Subjects will be managed by their PCP thereafter.
3. All spirometry test results and the subject's assessment at the time of the test will be uploaded into the subject's electronic health record for future reference.

D) Outcome Measures:

1. Primary outcome:

- (i) Accurate classification of patient as having COPD and/or asthma
- (ii) All-cause and respiratory related, acute care outpatient visits, ED visits, and hospitalizations

2. Secondary outcome:

- (i) Appropriate use of respiratory medications based on guidelines
- (ii) Use of other diagnostic testing: ECG, echocardiograms, CT/CXR, stress testing, cardiac catheterization, other pulmonary function tests
- (iii) Initiation of guideline based therapy
- (iv) Quality of life measures

E) Data collection and follow-up

1) Baseline data collection obtained at visit zero (V_0), in addition to those listed under intervention and usual care:

- 1. Demographic data (gender, age, self-reported race)
- 2. SES related measures: median household income
- 3. Level of education
- 4. Type of health insurance or self-pay
- 5. Up to two emergency contacts information
- 6. List of current respiratory medications from subject's pharmacy and verification with patient
- 7. Co-morbidities
- 8. History of prior ED visits or hospitalizations in the past one year with associated cause
- 9. EQ-5D 5L +B Bolt-on
- 10. SF-36 short form
- 11. Social support survey

2) All subjects will have their medical charts reviewed every 3 months after the initial visit (MR_1 , MR_2 , MR_3 , MR_4) up to one year. These electronic medical chart reviews will be used to obtain follow-up data since last study contact.

- 1. Change in type of health insurance or self-pay
- 2. List of current respiratory medications from subject's pharmacy and verification with patient
- 3. Use of diagnostic testing: ECG, echocardiograms, CT/CXR, stress testing, cardiac catheterization, other pulmonary function tests
- 4. Any ED visits or hospitalizations or acute outpatient care visit and associated cause.
- 5. Healthcare utilization outside of U of I system (e.g. testing such as spirometry, ED and hospitalizations) if available through scanned records

3) All subjects will be contacted every 3 months after the initial visit via telephone (T_1 , T_2 , T_3 , T_4) up to one year; or they will be given the option to complete in person based on subject's convenience, for example they have a doctor appointment near time of study follow-up. These phone calls will be used to obtain follow-up data since last study contact. A reminder post-card will be mailed to the subjects a month before the next telephone contact.

- 1. Change in type of health insurance or self-pay

2. List of current respiratory medications from subject's pharmacy and verification with patient
3. Use of diagnostic testing: ECG, echocardiograms, CT/CXR, stress testing, cardiac catheterization, other pulmonary function tests
4. Any ED visits or hospitalizations or acute outpatient care visit and associated cause.
5. Healthcare utilization outside of U of I system (e.g. testing such as ancillary testing, ED and hospitalizations)
6. mMRC
7. A respiratory exacerbation history
8. EQ-5D 5L +B Bolt-on
9. SF-36 short form (at 3, 6 and 12 months)
10. Social support survey (at 6 months and 12 months)

F) Monetary compensation of subjects

1. PCP compensation:

UI Health and MSHC PCPs will receive \$95 in cash after completion of the education session. For CCHHS PCPs, the Division or Department will receive a total of \$95 per participant to be part of the divisional fund to be used by the PCP at their discretion as allowed by their institution.

2. Patient subject compensation:

Baseline visit (Vo):

Same for Intervention and usual care groups: Subjects will be provided \$75 in cash for completing the initial study visit.

Telephone contact (T₁-T₃):

Same for Intervention and usual care groups. Subjects who choose to complete the follow-up in person or via telephone will receive \$20 in cash at the time of the visit or at a later specified time that is convenient for the subject.

Final contact (T₄):

Intervention: Subjects will receive \$95 in cash at the time of their last visit in-person.

Usual Care Group: Subjects will receive \$95 in cash at the completion of the 1 year spirometry and follow-up.

Additional spirometry visits after de-escalation of therapy:

Same for Intervention and usual care groups (except the intervention group will receive this near the beginning of the study and usual care group will receive this near the end of the study): Subjects will be provided a \$50 in cash for each additional spirometry visit.

2.A. Provision to compensation: If human subject receives over \$200.00 within one (1) calendar year, it is incumbent for the study staff to obtain the subject's social security number based on the OBFS guidelines. However, if human subject receives a total under \$200.00 within the calendar there is no need to obtain social security number from the human subject.

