5. STATISTICAL ANALYSES

All data will be stored in a secure, locked location. Data will be entered and managed through the Research Electronic Data Capture (REDCap). REDCap is a secure web-based application for building and managing online databases. REDCap is provided by

the CCTS Design Analysis Core. Data will be analyzed for clinical effectiveness using intention-to-treat principles.⁶⁹⁻⁷¹ For **Aim 1**, we will evaluate the misdiagnosis rates of the intervened and usual care groups separately at the first visit. Then compare rates between groups by using a generalized linear mixed model for binary outcome with two cluster levels, PCP and hospital, to account for the dependence within clusters. For the **Aim 2**, to investigate the impact of the misdiagnosis over time (4 time points: 0, 3, 6, 9, 12 months) on the quality of life and healthcare utilization, we will fit generalized linear mixed models with time, group, and their interaction as the main predictors. Two cluster levels, PCP and hospital, will be specified in the model to account for the dependence within clusters^{72,73} and an appropriate link function will be used for each outcome. Clinical important confounders will also be adjusted in the models. Before these analyses we will use descriptive statistics to describe the sample, and any assumption behind each statistical method will be examined during the analysis. A two-sided p-value less than 0.05 would be considered as statistical significance. All the analyses will be conducted by using SAS 9.2 (SAS Inst., Cary, NC).

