For **Aim 3: Costs**: The intervention costs for the study include the cost of the spirometry test, the time of the CHW/health promoter, and time of pulmonologist to provide periodic oversight of spirometry validity. In addition to estimating the costs associated with the intervention it will be important to measure the healthcare utilization for participants included in the study. It is possible that the intervention leads to use of other healthcare resources, particularly if the patient is determined to be free of respiratory disease. Therefore, we will measure both respiratory-related and overall healthcare costs. To measure these costs, we will determine overall healthcare utilization and apply unit costs to each of the events. Using chart reviews, we will examine healthcare utilization during the follow-up period. We will categorize healthcare utilization into either respiratory-related or all other healthcare use. We will apply standardized prices to each of the utilization components to estimate the overall and respiratory-related healthcare resource use during the study period. The standardize prices will be based on either the National Committee for Quality Assurance standardize price list for their relative resource use measure or Medicare reimbursement rates. For medications, we will rely on average wholesale price of medications to assign an average price to each of the COPD and asthma-related medications.

Cost-Effectiveness: The secondary outcome measures included in the study will be used to estimate the effectiveness to be used in the cost-utility analysis. We will use responses to the EQ5D to estimate patient utility and use that in calculation of quality-adjusted life-years (QALY). The area under the curve will be compared between the two groups and the difference will be the incremental effect used in the cost-utility analysis.

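### No stratification is stated for PCP randomization, and Aim 3 names no health-system term to absorb the chance imbalance that can result

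*Combined protocol and SAP*

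**What the plan says.** The unit of randomization is the provider. Section 1 states: "Providers will be randomized and their patients who fulfill the inclusion criteria will receive the intervention or be in the usual care group". Section 4.A adds that "PCPs who consented to participate in the study and completed the education session will be randomized", and describes the two arms. Neither section, nor any other, gives a ratio, block size, stratum, matching factor or minimization factor.

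Section 3 sets the planned numbers. The investigators "estimate a total maximum recruitment of 80 eligible PCPs from all sites", made up of "approximately 50 PCPs from UI Health and MSHC sites and approximately 30 PCPs from CCHHS". Patient recruitment is fixed by system: "A total of 250 from UI Health and MSHC sites and a total of 250 from CCHHS site".

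In section 5, Aim 1 uses a "generalized linear mixed model for binary outcome with two cluster levels, PCP and hospital, to account for the dependence within clusters". Aim 2 has the same two levels plus clinical confounders that are not named. The Aim 3 text carries no such levels. For QALYs, "The area under the curve will be compared between the two groups and the difference will be the incremental effect"; the cost numerator is likewise the difference between groups. Confidence limits for the ICER come from bootstrapping, and the resampling unit is not given.

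**The concern.** Patient numbers are balanced by health system across the trial, but nothing stated balances them by system between the arms. Randomizing a few dozen providers, each bringing several patients, gives much coarser control over system mix than randomizing 500 individuals.

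The plan itself treats hospital as worth modelling for Aims 1 and 2, then names no such term for Aim 3. If patients in the two systems differ in utilization, in EQ-5D, or in how fully their care is captured, an uneven system mix passes straight into the incremental cost and the incremental QALY. Capture could differ: section 7 has each institution's staff review its own records, and the follow-up items on outside care in section 4.E refer only to care outside the U of I system, although half the patients are to come from CCHHS.

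**Working it through.** The plan states no imbalance figure, ICC or power calculation, so there is nothing of its own to reproduce beyond 50 + 30 = 80 PCPs and 250 + 250 = 500 patients, which agree.

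**Inputs from section 3.** Patients per PCP: 250/50 = 5.0 at UI Health/MSHC and 250/30 = 8.33 at CCHHS. Assumed, because not stated: a 1:1 ratio, allocation that ignores system, and equal yield per PCP within a system.

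**Distribution.** Let x be the number of CCHHS PCPs in the intervention arm under a fixed 40:40 split. Then x is hypergeometric (80 PCPs, 30 from CCHHS, 40 drawn), with mean 15 and SD √(40 × 30/80 × 50/80 × 40/79) = 2.18.

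- CCHHS share, intervention: 8.33x / [8.33x + 5(40 − x)]
- CCHHS share, usual care: 8.33(30 − x) / [8.33(30 − x) + 5(10 + x)]

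Example, x = 19: 158.3/(158.3 + 105) = 60.1% against 91.7/(91.7 + 145) = 38.7%, a gap of 21.4 points.

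**Results** for the between-arm difference in CCHHS share:

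| Allocation | SD (points) | Gap ≥ 10 | Gap ≥ 20 |
|---|---|---|---|
| 80 PCPs, 40:40, ignoring system | 11.6 | 49% | 10.5% |
| 80 PCPs, coin flip for each | 11.7 | 40% | 9% |
| 40 PCPs (25 and 15), 20:20 | 16.6 | 51% | 19% |
| 500 patients individually, 250:250 | 4.5 | 2.5% | < 0.1% |

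The 49% and 40% differ partly because the distribution is discrete: a 17 to 13 split of CCHHS PCPs under 40:40 gives 10.7 points, just over the threshold. Under the coin flip, the intervention arm has a 95% range of about 193 to 307 of the 500 patients.

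**What drives it.** With 40 PCPs per system and 6.25 patients each (500/80), the 40:40 SD would still be 11.25 points. The small number of clusters is the cause; the 5.0 against 8.33 contrast adds little.

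**After stratifying by system** (15:15 and 25:25). With equal yield per PCP the gap is 0. With uneven yield (gamma-distributed, assumed CV 0.5, simulated), the SD is 5.7 points against 13.0 unstratified. A gap of at least 10 points then occurs in 8% against 45% of allocations, and of at least 20 in 0.05% against 12%. Over CV 0.3 to 0.7, the chance of at least 10 points is 0.4% to 22% stratified, against 41% to 48% unstratified.

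**Effect on Aim 3.** Error in incremental cost = (difference in mean cost between systems) × (difference in share). The first factor is not in the documents. If it were $500 to $2,000 per patient, the SD of the error would be 0.1165 × 500 = $58 to 0.1165 × 2,000 = $233 per patient. The same product form applies to QALYs.

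**Precision once system is a fixed term** (independent patients, common effect). Relative variance = (500/4) / Σ(n_int × n_uc / n) over systems, where n_int and n_uc are the intervention and usual-care patients in a system and n is their total. For the 19 to 11 split: 158.3 × 91.7/250 + 105 × 145/250 = 58.1 + 60.9 = 119.0, and 125/119.0 = 1.05. Averaged over allocations, the loss is 1.5% (40:40) or 2.8% (coin flip).

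**The case against.** The case on the other side is substantial.

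- A reader might infer that the trial uses simple, unrestricted randomization. The protocol does not say that. It is silent, and a restricted list may exist; the figures above describe allocation that ignores system.
- A reader might infer a biased comparison. Over repeated allocations the expected imbalance is zero, and no passage reports any system difference in patients, use or referral. All sites share one electronic record system (section 3), so separate chart reviewers do not by themselves show different capture.
- A reader might infer that local prices leak into Aim 3. Section 5 applies standardized prices and average wholesale drug prices, which removes unit-price differences and leaves only differences in recorded use.
- A reader might extend the problem to every aim. Aims 1 and 2 already have a hospital level, and with a fixed system term the average precision lost by not stratifying is only 1.5% to 2.8%.

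All of this stands and limits the point. Two things remain. The Aim 3 description names no system or PCP term; its general reference to recommended cost-effectiveness methods does not supply one. And hospital appears to have only two levels: if fitted as random, its variance would be poorly estimated, so a fixed term is the more reliable protection in Aim 2 as well.

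**Conclusion.** The point holds as a worthwhile, inexpensive improvement to both design and analysis, centred on Aim 3. If allocation ignores system, a gap of 10 points or more in CCHHS share between arms is close to an even chance (40% to 49%), and one of 20 points or more has about a one-in-ten chance (9% to 10.5%). These figures rest on the planned 50/30 PCPs and 250/250 patients, a 1:1 ratio and equal yield within system. Since 80 PCPs is a maximum, fewer would make it worse.

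What such a gap does to the incremental cost or QALY depends on between-system differences that the documents do not give; the dollar range is an illustration only. The documents support neither a finding of bias nor a material loss of precision in Aims 1 and 2.

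**What to change.** 1. In section 4.A, state that PCPs are randomized 1:1 in permuted blocks within health system (UI Health/MSHC; CCHHS), and within clinic only where PCP numbers allow. Clinic-level PCP counts are not given, so a full set of clinic strata cannot be shown to be feasible, and small clinics may need merging.
2. In section 5, include health system as a fixed term in the Aim 2 models and in the Aim 3 cost and QALY comparisons.
3. Bootstrap the ICER by resampling PCPs within system and arm.

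For PCPs already randomized, a new list repairs nothing and only the analysis changes apply; these should be fixed before outcome data are compared by arm.

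The cost is one allocation list and one added model term, with no extra patients, visits or staff. Some imbalance will remain where PCPs yield unequal numbers of patients, which is why the analysis term is needed as well as the strata.
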